8.1.2 Serious Adverse Events

A serious adverse event (SAE) or reaction is any untoward occurrence that at any dose: Results in death, is life-threatening, requires inpatient hospitalization or prolongation of existing hospitalization, results in persistent or significant disability/incapacity, is a congenital abnormality or a birth defect. The term "life-threatening" in the definition of "serious" refers to an event in which the participant was at risk of death at the time of the event; it does not refer to an event which hypothetically might have caused death if it were more severe.

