8.2 Assessment of an Adverse Event

8.2.1 Relationship (Causality/Relatedness)

The causality assessment is the determination, according to the investigator's clinical judgment, of the existence of a reasonable possibility that the study drug (IP) caused or contributed to an adverse event. If the investigator or delegated sub-investigator is unsure about whether or not the study drug caused or is related to the event, then the event will be handled as "related" to the study drug for reporting purposes of the trial. If the causality assessment is

"unknown but not related" to the study drug, this should be clearly documented in the source documents.

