8.6 Reporting and Entry Timelines

Study investigators will report SAEs to the sponsor within the following timelines: All deaths and immediately life-threatening events, whether related or unrelated, will be recorded and reported to the sponsor within 24 hours of site awareness. Serious adverse events other than death and immediately life-threatening events, regardless of relationship, will be reported to the sponsor within 72 hours of site awareness. Adverse event information will be entered into the CRF in a timely manner and no later than 15 days from the time the investigator becomes aware of the event. Serious adverse event information will be entered into the CRF in a timely manner/within 72 hours from the time the investigator becomes aware of the event.

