8.7 Evaluation of Adverse Events and Safety Questionnaires

Local and systemic AE will be evaluated within 48 hours to 14 days and 1 month post third dose. Local adverse events include pain at the injection site, redness, and swelling. Systemic adverse events include fever, fatigue, headache, chills, vomiting, diarrhea, new or worsened muscle pain, and new or worsened joint pain. Serious adverse events (SAE) will be recorded and investigated and questions will be adapted from the report of Adverse Event Following Immunization (AEFI) from Public Health Ontario, including local reactions at the injection site, symptoms (fever, chills, fatigue, nausea/vomiting, diarrhea, muscle pain, joint pains and other adverse events). Participants will be advised that acetaminophen may reduce vaccine side-effects but will not actively be counselled to medicate, but usage will be recorded. Due to kidney disease, anti-inflammatory medication will be discouraged. A recent study of heterologous prime-boost found increased adverse events with heterologous vaccination but no hospitalizations were recorded, and most adverse events occurred within 48 hours of vaccination.²⁰

In Ontario, all chronic dialysis patients are currently being tracked for serious adverse events using the COVID-19 vaccine tracker although this had not detected any serious adverse events to date. This customized Excel spreadsheet is pre-populated by the Ontario Renal Network (ORN) and completed by renal programs monthly (submitted securely via Tumbleweed systems). Adverse events related to vaccination are also tracked in PROMIS (BC) which has detailed clinical records on their patients. Coordinators will conduct a questionnaire to inquire about local and systemic symptoms related to the vaccine. Other rare adverse events will be captured using detailed descriptions. Questionnaires will be conducted 48 hours -14 days, and 1 month after the booster vaccination dose. Individuals participating in the pilot study have had side effects after the first two doses of vaccine recorded. SAEs are defined using the Health Canada definition as

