those resulting in hospitalization admission or prolongation of existing hospitalization, resulting in persistent or significant disability or incapacity, is life-threatening, or resulting in death and definitely or probably associated with vaccination in the opinion of their nephrologist. The provincial data collection includes reasons for vaccine hesitancy or refusal which could inform education for specific groups. In addition, renal programs in Ontario are currently tracking all infections, including the 3 reported variants (B117, B1351, P1, and others).

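### Section 8.7 builds vaccine attribution into the SAE definition, in conflict with 8.1.2 and 8.6; the events exposed are mainly non-life-threatening admissions and disability

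*Combined protocol and SAP*

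**What the plan says.** Section 8.1.2 defines an SAE by what happened to the participant: "Results in death, is life-threatening, requires inpatient hospitalization or prolongation of existing hospitalization, results in persistent or significant disability/incapacity", or a congenital abnormality or birth defect. It sets no causality condition.

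Section 8.6 sets the time limits. For the gravest events: "All deaths and immediately life-threatening events, whether related or unrelated, will be recorded and reported to the sponsor within 24 hours". For the rest: "Serious adverse events other than death and immediately life-threatening events, regardless of relationship, will be reported to the sponsor within 72 hours". It adds that "Serious adverse event information will be entered into the CRF in a timely manner/within 72 hours", whereas ordinary adverse events have 15 days for CRF entry.

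Section 8.2.1 gives the causality judgment to the investigator or a delegate. Its rule for doubtful cases begins "If the investigator or delegated sub-investigator is unsure about whether or not the study drug caused or is related to the event" and goes on to treat such an event as related for reporting.

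Section 8.7 says in its first paragraph that "Serious adverse events (SAE) will be recorded and investigated". Its second paragraph then gives a definition of its own. That definition opens "SAEs are defined using the Health Canada definition as", lists hospital admission or prolongation, disability, threat to life and death, and closes with the condition "definitely or probably associated with vaccination in the opinion of their nephrologist".

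Section 8.3 lists occurrences that do not count as adverse events and need not be recorded. Among them are events put down to the underlying disease and events frequent in this population whatever the product. It carves out nothing for serious events.

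**The concern.** Seriousness and relatedness are separate judgments, and 8.1.2, 8.2.1 and 8.6 keep them apart. Section 8.7 merges them. Under its wording an event must pass a relatedness test before it earns the SAE label, and most of the reporting duties for serious events are keyed to that label. It also moves the judgment to the patient's nephrologist, who may or may not be the investigator.

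Adverse events related to the third dose are a secondary objective (3.2), the safety committee reviews adverse events (8.8), and the first stopping rule in 10.4 depends on them. Sites working from different definitions could classify the same admission differently and send it to the sponsor at different speeds.

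**Working it through.** There is no figure in the plan to reproduce, and the only numbers are time limits. The check is a comparison of sections.

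| Section | What triggers the rule | Relationship needed | Who judges it |
|---|---|---|---|
| 8.1.2 | Serious outcome | None | Not applicable |
| 8.6, 24-hour rule | Death or immediate threat to life, named directly | None | Not applicable |
| 8.6, 72-hour rules | The SAE label | None | Not applicable |
| 8.2.1 | Causality assessment for reporting | Unsure counts as related | Investigator or delegated sub-investigator |
| 8.7 | Serious outcome plus attribution | Definite or probable | The patient's nephrologist |

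Cases put through the table:

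1. *A non-life-threatening admission judged unrelated or only possibly related.* It is an SAE under 8.1.2 and reportable under 8.6. It is not an SAE under 8.7 if the clause covers all the listed outcomes.
2. *The same admission with uncertain causality.* It is handled as related under 8.2.1. It fails the definite-or-probable test in 8.7.
3. *A death judged unrelated.* It is not an SAE under 8.7. Section 8.6 still requires it to be recorded and reported within 24 hours, because that rule names deaths and does not rely on the SAE label. The same holds for immediately life-threatening events.

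What remains exposed is mainly other admissions, prolonged admissions and disability judged less than probably related.

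Consequence for that set: an event that loses the SAE label is still an adverse event under 8.1.1, which does not depend on relatedness. CRF entry is then due within 15 days instead of 72 hours. Since 72 h ÷ 24 = 3 days, the entry limit is 15 − 3 = 12 days later. The 72-hour sponsor notification would also not apply, and 8.6 sets no sponsor-notification limit for ordinary adverse events.

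Two narrower readings of 8.7:

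- *Grammar.* The attribution clause follows the word for death and could attach to death alone. Cases 1 and 2 then disappear. The conflict moves to deaths, where 8.6 is explicit that relationship is irrelevant.
- *Context.* The paragraph opens with the Ontario and British Columbia tracking systems, and the sentence after the definition concerns provincial data collection. The definition could describe the tracker only. But sentences on the trial questionnaires and the pilot study come between, and no words confine it to the tracker.

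Secondary check, 8.3 against 8.6: an admission from a cause common in dialysis patients can fall under the 8.3 exemption and need no recording. If it meets 8.1.2, then 8.6 requires it to be reported and entered in the CRF. For deaths and immediately life-threatening events 8.6 expressly requires recording, so the conflict of wording is plainest there, although 8.6 also protects those events.

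**The case against.** The strongest defence is that the protocol's intention is clear. An instruction in 8.6 to report SAEs whatever their relationship would be pointless if relatedness were already part of being an SAE. The nephrologist as judge and the surrounding provincial text also suggest that the clause belongs to the tracker. Section 8.4.1 and the first paragraph of 8.7 require SAEs to be recorded as well.

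Much of this stands: the outcome-based definition is evidently intended, and the tracker reading is plausible. It does not remove the problem. The recording and 72-hour rules use the term SAE, so they cannot settle what the term means, and 8.7 offers an unrestricted competing definition.

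Three stronger readings are tempting and are not supported:

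- A reader might infer that serious events would go unrecorded because of 8.7. They remain adverse events under 8.1.1 with a CRF deadline, so the 8.7 failure is one of label and timing. Only the separate 8.3 exemption could remove a record.
- A reader might infer that expedited reports would be missed. The test in 8.4.2 asks whether an event is serious, unexpected and not ruled out as related. It does not depend on the 8.7 label.
- A reader might infer that sites would use 8.3 to drop acute kidney or cardiovascular injury. Section 8.4.5 names these as events of special interest, and the relevant limb of 8.3 is limited to events occurring independently of the product. How sites would act is conjecture.

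**Conclusion.** The contradiction between 8.7 and both 8.1.2 and 8.6 is real, as is the mismatch with 8.2.1 on who judges causality and how doubt is handled. The 8.3 exemption is a lesser conflict with 8.6 for serious events.

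The size is small. If the 8.7 clause applies to every listed outcome and a site follows it literally, the exposed events are mainly the non-life-threatening ones identified above, and the effect is slower handling as ordinary adverse events. If the clause attaches only to death, or describes only the tracker, what is left is a wording conflict or an unclear scope. The documents give no SAE rate, so neither a count nor a proportion can be stated.

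A reader might go further and infer that the comparison of the vaccines is compromised. The documents do not support that: the primary outcome is serological, and nothing in the text makes misclassification differ by arm. This is a minor safety-reporting inconsistency that should be cleared up.

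**What to change.** Reconcile the sections to a single SAE definition, with two edits:

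- In 8.7, either delete the attribution clause and refer to 8.1.2, or state that the clause describes only what the provincial tracker collects and does not define an SAE for the trial.
- In 8.3, state that the recording exemption does not apply to any event meeting 8.1.2.

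No change to 8.2.1 is needed, since it already requires a causality assessment.

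The cost is protocol wording, plus slightly more event entry within the collection period in 8.5, which runs to 30 days after the last dose. Section 8.6 already requires that entry for serious events. Sample size, visits and the statistical analysis do not change.

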8.8 Data Safety Monitoring Committee (DSMB)

The data safety monitoring committee will include Nephrologists, an infectious disease specialist, Public Health Specialist, and experts in clinical trials. The DSMC will review summary data and adverse events several times early in the trial and subsequently will meet at approximately 6 months and 12 months following the third dose. The purpose of the DSMC will be to review safety concerns and review external data that may have bearing on the design of or decision to continue the trial.

8.9 General Trial Conduct Considerations

8.9.1 Protocol Deviation

We will allow a 7 day window for collection of blood samples for the primary outcome at 1 month. During the later blood collection period, we will allow a 15 day window for collection of blood samples or the blood collection will be deferred until the next scheduled time point. It is the responsibility of the investigator to ensure that only investigative procedures, as outlined in this

protocol are performed on study participants; the occurrence of deviations from the protocol or SOPs are limited; and compliance with the regulations is maintained. Planned deviations from the protocol must not be implemented without prior agreement from the sponsor and approval from the local REB/ethics committee (EC), as required, unless to eliminate an immediate hazard to a participant. Planned or unplanned deviations may occur on the part of the participant, the investigator, or study research team. In resolution to a deviation, corrective/preventative actions are to be developed and implemented in a timely manner. Protocol deviations will be documented and reported as required and assessed where necessary during analysis.

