3.2 Secondary Objectives/Outcomes

1. Measurement of Anti-Spike, Anti-NP antibodies, and SARS-CoV-2 specific neutralization at 1 month (30 days) following third dose of vaccine.
2. Determine the effect of a third dose of COVID-19 vaccine on humoral immune response in hemodialysis patients who did not attain convalescent serum levels or exhibiting declining antibody levels below convalescent serum levels of Anti-RBD through measurement of Anti-Spike, Anti-RBD, and Anti-NP antibodies at 3 months, 6 months and 12 months following booster dosage.
3. In a subset of participants, assess cellular immunity through flow cytometry on PBMC and single-cell RNA sequencing prior to, one month, and 6 months following vaccine booster.
4. Evaluate adverse events related to third dose of vaccine through a questionnaire within 48 hours to 14 days and 30 days following third vaccine dose.
5. Differences in COVID-19 infections, symptomatic COVID-19 infections, hospitalization, and death between study groups.

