Prior to receiving a third vaccine dose, quantitative SARS-CoV-2 IgG antibody levels against the full-length spike protein S1 domain, and Receptor Binding Domain (RBD) to assess humoral response will be measured and Anti-SARS-CoV-2 nucleocapsid protein to measure evidence of prior COVID-19 infection. In addition, we will isolate peripheral blood mononuclear cells in a subset to evaluate cellular immune response, however this will only be performed at University Health Network and Sunnybrook Health Sciences Centre as only these centres have the capacity for processing these samples. A neutralization antibody assay developed by the [name] lab will also be used to assess for viral neutralization prior to booster dose at 1 month (30 days) post third dose of vaccine.

[figure not shown]

Figure 2: Four study groups in the BOOST KIDNEY study. Study participants will be randomized 1:1 after stratification by initial vaccine type.

Following the intervention, SARS-CoV-2 antibodies will be measured 1 month, 3 months, 6 months and 12 months post booster vaccination. Neutralizing antibodies will be measured at baseline and 1 month post third dose of booster vaccine. Cellular immunity in a subset will be evaluated at baseline, 1 month and 6 months post third dose of booster vaccine. Adverse events related to third dose of vaccination will be surveyed in the 14 day period following third dose of vaccine, and again 1 month following third dose. The study protocol may be altered if booster doses become available that are intended to target new SARS-CoV-2 variants. Furthermore, the study design will be adaptive, as if patients do not respond to a third dose of vaccine the study protocol may be amended to consider other vaccine booster interventions. All study practices will follow social distancing measures currently recommended by Public Health authorities.

5 PARTICIPANT SELECTION and WITHDRAWAL

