10.5.2 Statistical Analysis of Secondary Outcomes

Secondary outcomes will include the proportion of patients who attain Anti-Spike median convalescent serum at 1 month (30 days) following third dose of vaccine. Differences in relative antibody levels (Anti-Spike and Anti-RBD) and neutralizing antibodies between study groups will be assessed through the Mann-Whitney test. The relative levels of antibodies will be tracked

longitudinally for each patient permitting analysis of SARS-CoV-2 antibody kinetics following vaccination and will be assessed through a mixed-effects repeated measures model with random intercepts and fixed covariates following log transformation of relative ratios, which will be exploratory. Differences in serial levels in relative antibody levels will be compared through a mixed effects model as above. Similar to the primary outcome, those with a new positive Anti-NP serologic test or COVID-19 nasopharyngeal swab during the study will be excluded from analysis. An intention to treat analysis will be followed, although an exploratory per protocol analysis may also be reported.

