13.3.2 Risks

All potential risks will be explained to the participants. The greatest risks to this study include the possibility for increased reactogenicity or adverse effects following a booster dose of vaccine that may make the patient feel unwell. Larger studies on safety of a third dose are not widely available, but early studies in solid organ transplant patient have demonstrated acceptable tolerability and generally low incidence of severe adverse effects, therefore we expect that this risk will be present but not high. The risk of phlebotomy is low as the blood volume obtained from patients is minimal, and does not require additional blood draws from hemodialysis patients as these blood samples will be collected during routine hemodialysis care through pre-existing vascular access. Peritoneal dialysis and CKD patients have a small risk of bruising due to blood draws.

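### Section 8.9.1 replaces an out-of-window 3- or 6-month sample with the next visit and gives a late 12-month sample no destination, so obtainable secondary-outcome data are lost by rule

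*Combined protocol and SAP*

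**What the plan says.** Section 8.9.1 (Protocol Deviation) treats two sampling periods differently.

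- Month 1: "We will allow a 7 day window for collection of blood samples for the primary outcome at 1 month". No deferral clause is attached to this sample.
- Later visits: "During the later blood collection period, we will allow a 15 day window for collection of blood samples", and otherwise "the blood collection will be deferred until the next scheduled time point".

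The schedule is in Section 4.1: "SARS-CoV-2 antibodies will be measured 1 month, 3 months, 6 months and 12 months post booster vaccination". Table 1 and Appendix A both end at 12 months. The later samples serve secondary objective 2 in Section 3.2, which covers Anti-Spike, Anti-RBD and "Anti-NP antibodies at 3 months, 6 months and 12 months following booster dosage". Section 10.3 plans analyses at each of those times.

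Section 10.5.2 compares antibody levels between groups with the Mann-Whitney test, without naming the time points. It has the longitudinal levels "assessed through a mixed-effects repeated measures model with random intercepts and fixed covariates following log transformation of relative ratios, which will be exploratory". How time enters that model is not stated. No missing-data method is given for the later visits, and the 10% loss allowance in Section 10.2 covers the 1-month follow-up only.

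**The concern.** A visit window normally decides how a sample is labelled and analysed. Here it also decides whether the sample is taken at all. A participant seen one day after the window closes is not bled until the next visit, and at 12 months there is no next visit.

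Sites have little room to work around this. Section 8.9.1 also confines investigators to the procedures that the protocol describes, and requires sponsor agreement and, as required, ethics approval before a planned deviation.

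What is at stake is the antibody curve after month 1. Section 2.2 reports declining antibody levels by 13 weeks in the sponsor's own hemodialysis cohort, so a skipped 3-month draw falls where the plan itself expects change.

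**Working it through.** The plan gives no figure for missed windows, so there is none to reproduce. The check has two parts.

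**1. Where the rule leaves no permitted draw.** Visit days are assumed to be 91, 183 and 365 after the booster. The text does not say whether 15 days means 15 either side or 15 in all, so both readings are shown. The second is taken as centred, 7 days either side of the visit day (7 + 1 + 7 = 15).

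| Reading | 3 months | 6 months | 12 months | Gap 3 to 6 | Gap 6 to 12 | After month 12 |
|---|---|---|---|---|---|---|
| ±15 days | 76–106 | 168–198 | 350–380 | 168 − 106 = 62 days | 350 − 198 = 152 days | nothing after day 380 |
| 15 days in total | 84–98 | 176–190 | 358–372 | 176 − 98 = 78 days | 358 − 190 = 168 days | nothing after day 372 |

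On either reading, a missed 3-month draw leaves that participant with nothing between months 1 and 6. A missed 6-month draw leaves nothing between months 3 and 12. A missed 12-month draw is not replaced.

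**2. Precision at one visit.** Let p be the share of samples at a visit lost to the rule. The documents give no value, so 5%, 10% and 15% are assumed.

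If only the samples actually taken are used, the standard error of that visit's mean is multiplied by 1/√(1 − p):

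- p = 5%: 1/√0.95 = 1.026, a rise of 2.6%
- p = 10%: 1/√0.90 = 1.054, a rise of 5.4%
- p = 15%: 1/√0.85 = 1.085, a rise of 8.5%

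A mixed model loses less, because the participant's other visits carry information about the missing one. If those visits explain a share R² of the variance at the missed visit, and data are missing at random, the multiplier is √((1 − p·R²)/(1 − p)). At p = 10%, with R² assumed between 30% and 80%:

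- R² = 30%: √(0.97/0.90) = 1.038, a rise of 3.8%
- R² = 80%: √(0.92/0.90) = 1.011, a rise of 1.1%

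Both sets of figures are upper limits on what late sampling could recover, because it would not bring back samples lost to death or withdrawal.

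**The case against.** The strongest defence is that a bounded window keeps visits comparable. On a declining curve, samples taken at scattered times add timing noise, and the Mann-Whitney test cannot take a day covariate to adjust for it. This stands, and it shapes the fix: late draws need an upper limit and should stay out of the main visit-specific tests. It does not justify forgoing the sample, because the mixed model can use it at its true date.

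A second defence is that few windows will be missed. Section 2.1 has facility dialysis patients attending at least three times a week, which is about 6 sessions in 15 days (15/7 × 3 = 6.4), and Section 13.3.2 says of hemodialysis patients that "these blood samples will be collected during routine hemodialysis care through pre-existing vascular access". This also stands for in-centre patients. It is weaker for peritoneal dialysis and non-dialysis CKD participants, for whom Section 13.3.2 describes a separate blood draw. It also leaves the 12-month gap in place.

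A reader might go further and infer that missed windows fall mainly on the sickest participants, so that the remaining curve overstates durability. The documents do not support this. They give no rate or pattern of missed windows. The one illness-related non-collection they describe is active COVID-19 (Section 7.3), and participants who develop COVID-19 are excluded from the analysis anyway (Sections 7.2.3, 10.5.1 and 10.5.2). The attendance pattern suggests that misses could fall as much on home-dialysis or non-dialysis participants. Bias in the mixed model would need missingness that depends on unobserved levels even after the observed ones are used. A distorted comparison between arms would further need it to act differently in the two arms.

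**Conclusion.** The point holds as a defect in a rule for a secondary outcome. Followed as written, Section 8.9.1 forgoes 3- and 6-month samples that could still be taken, and it says nothing workable about a late 12-month sample.

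Three limits apply:

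- The primary outcome at 1 month is not affected.
- Only the missed visit is lost for that participant. It would be too strong to say that the durability data as a whole are lost.
- The longitudinal model is labelled exploratory.

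The precision cost is modest: at most 2.6%, 5.4% or 8.5% on the single-visit complete-case standard error at assumed losses of 5%, 10% or 15%, and less in the mixed model. No size or direction of bias can be given from the documents. The general statement in Section 8.9.1 that deviations will be assessed during analysis, and the final analysis plan still to be developed under Section 10.5, do not close the gap, because a sample never drawn cannot be restored at analysis.

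**What to change.** Replace the deferral clause in Section 8.9.1 with wording such as:

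> If the window is missed, the sample is taken as soon as possible before the next visit's window opens (for 12 months, up to a stated limit after the window closes), and the actual date is recorded.

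Then:

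- State in Section 8.9.1 whether 15 days means ±15 or 15 in total.
- In Section 10.5.2, enter time in the mixed model as actual day since booster, on a continuous scale with its functional form specified, and include the late samples.
- Keep the visit-specific Mann-Whitney comparisons to in-window samples, and add the late samples in a sensitivity analysis.

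The cost is small. Section 7.3 already puts the collection date on the tube label, and it already lets sampling resume after COVID-19 precautions end, so delayed collection is not new to this protocol. The downsides are that a few samples fall off the nominal day and that some peritoneal dialysis and non-dialysis CKD participants need a late draw.
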